## 7.6.8 Electrocardiogram (ECG)

The 12-lead ECGs will be performed at screening and predose and 2 hours (±30 minutes) postdose on C1D1 and C2D1; they will be performed predose at all other time points on the dosing days and at the Treatment Termination visit as indicated. For each ECG parameter (heart rate, RR interval, PR interval, QRS duration, QT interval, and QT corrected for heart rate using Fridericia's formula (QTcF)), the mean of the available triplicate ECG values will be calculated.

ECG findings will be listed by subject and, if data permit, may be summarized as follows:

- The values and respective changes from baseline may be summarized by visit.
- Summaries may also be provided of the maximum post-baseline absolute QTcF and the maximum post-baseline increase in QTcF.

#### 7.6.9 ECOG Performance Status

Shift tables for ECOG from baseline to the worst grade, and from the baseline to the last available grade will be provided.

## 7.6.10 Echocardiogram / Multigated Acquisition (ECHO/MUGA)

Data will be preserved in a Study Data Tabulation Model (SDTM) dataset. No particular analysis will be conducted.

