7.7. Overdose Instructions

Record the actual dose of study drug administered in the source document and on the Dosing eCRF. Record any adverse clinical signs and symptoms associated with a potential overdose on the AE eCRFs. Report signs and symptoms of a potential overdose that meet SAE criteria

(defined in Section 10.1.2) to the Sponsor's Pharmacovigilance group or its designee within 24 hours from the time the investigator first becomes aware of the SAE (see Section 10.2.4). Treat any AE (including SAE) based on standard care for the specific signs and symptoms.

8. **RISKS/PRECAUTIONS**

Refer to the ASTX029 IB for the most current risks and precautions, as well as a list of potential AEs associated with ASTX029 therapy based on nonclinical toxicology studies and clinical findings with other investigational agents in this drug class.

This study represents the first use of ASTX029 in humans, and as with any investigational medicinal product (IMP), subjects may experience reactions or complications that are unknown and therefore unpredictable. Risks to subjects participating in this first evaluation of ASTX029 in a human clinical trial include the potential for adverse reactions.

Based on nonclinical toxicology studies with this molecule, and clinical findings with other investigational agents in this drug class (ERK inhibitors; ie, ulixertinib and GDC-0994) (Sullivan et al 2018; Li et al presentation 2017; Varga et al 2020; Infante et al abstract 2015; Infante et al presentation 2015), the ASTX029 mechanism of action may result in cutaneous AEs (eg, rash, pruritus, dry skin), GI AEs (eg, diarrhea, nausea, vomiting, and esophagitis), fatigue, peripheral and periorbital edema, LVEF decrease, potential arrhythmias, visual disturbances, and liver enzyme elevation.

The potential for these AEs warrants frequent monitoring of subjects participating in clinical trials of ASTX029 until the safety profile is further understood. In particular, clinical signs and/or symptoms of cutaneous, ocular, GI, and liver toxicities and LVEF decrease will be closely monitored, evaluated, and managed during the study (Appendix 4, Appendix 5, Appendix 6, Appendix 7, and Appendix 8 respectively).

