9.4.5. ECHO or MUGA Scan

Echo or MUGA scan assessments will be performed at screening, every 2 cycles for the first 4 cycles and every 4 cycles thereafter (\pm 7 days), and at the Tx Term visit as outlined in the schedules of events (Section 9.4.9). The same diagnostic method should be used throughout the study.

If a clinically significant abnormal finding is observed, the investigator will record it as part of the subject's medical history if it occurs prior to the start of study treatment on C1D1 and as an AE if it occurs after the commencement of study treatment.

9.4.6. **Ophthalmic Examination**

Subjects will be required to have a standard ophthalmic examination performed by an ophthalmologist at screening. The exam will include indirect fundoscopic evaluation, visual acuity (with correction), visual field examination, and tonometry with special attention to retinal abnormalities that are predisposing factors for RVO or CSR. Direct fundoscopy may be performed if indicated. Additional ophthalmic examinations (as detailed above) will be performed only as symptomatically warranted. In subjects with clinical suspicion of RVO or CSR, fluorescein angiography and/or optical coherence tomography are recommended.

If a clinically significant abnormal finding is observed, the investigator will record it as part of the subject's medical history if it occurs prior to the start of study treatment on C1D1 and as an AE if it occurs after the commencement of study treatment.

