11.7. Safety Analyses

Safety will be assessed by subject-reported and investigator-observed Aes along with concomitant medications, Pes, clinical laboratory tests (hematology, coagulation, serum

chemistry, and urinalysis), vital signs, ECOG performance status, ECGs, and ECHO/MUGA scans.

All Aes will be mapped to the appropriate System Organ Class (SOC) and Preferred Term (PT) according to the Medical Dictionary for Regulatory Activities (MedDRA). Severity of Aes will be graded using CTCAE v4.03 (Appendix 2). All Aes collected during the study will be presented in data listings. TEAEs are defined as events that first occur or worsen after the subject receives study drug on C1D1 until 30 days after the last dose of study treatment, or the start of an alternative anticancer treatment, whichever occurs first, to be defined in more detail in the statistical analysis plan. Summaries will be provided by SOC and PT for all Aes, Aes considered related to study treatment, SAEs, and related SAEs as follows based on the treatment period when the events occur. Similar summaries will also be generated by maximum severity. In addition, exposure to ASTX029, reasons for discontinuation, deaths, and causes of deaths will be tabulated.

The number and proportion of subjects who have DLTs, as defined in Section 7.4, will be summarized by cohort and regimen in Phase 1 Part A.

Laboratory values reported by different local labs will be listed. Shift tables will be provided for each graded laboratory test.

Concomitant medications are the medications taken with a start date on or after the start of the administration of study treatment (C1D1) or those with a start date before the start of the administration of study treatment (C1D1) and a stop date on or after the start of study drug administration (C1D1) as to be defined in more detail in the statistical analysis plan. Concomitant medication will be coded by the World Health Organization (WHO) Global List and summarized by therapeutic subgroup (Anatomical Therapeutic Chemical [ATC] level 2) and PT, sorted alphabetically, using counts and percentages.

Vital sign measurements will be summarized by visit using the proportion of subjects with each vital sign being too high or too low according to conventionally accepted vital sign normal ranges. Physical examination, ECOG performance status, and ECG findings will be listed in data listings or analyzed with summary tables.

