APPENDIX 8. DOSE MODIFICATION FOR DECREASE IN LEFT VENTRICULAR EJECTION FRACTION

Decreases of LVEF have been observed in patients receiving the MEK inhibitors trametinib (Mekinist USPI) and cobimetinib (Cotellic USPI) and the ERK inhibitor GDC-0994 (Varga et al 2020). ECHO or MUGA scans will be performed to assess cardiac ejection fraction in regular intervals as outlined in the schedule of events tables (Table 11 and Table 12).

Suggested guidelines regarding management and criteria for adjusting, withholding, and discontinuing study treatment for LVEF decrease are provided in Table 18. In the event that institutional standard practice differs from these suggested guidelines, institutional practices may be followed with best clinical judgement applied.

LVEF Decrease (%)	Action and Dose Modification	
Resting LVEF 49% to 40%; absolute decrease of >10% but <19% in LVEF from baseline and LVEF below the institution's LLN	 Interrupt study treatment and perform ECHO within 3 weeks. If ECHO recovers within 3 weeks: Consult with the Sponsor's medical monitor and request approval to restart ASTX029 dosing. If approval is obtained, restart at a lower dose level. If ASTX029 is restarted, repeat ECHO after 3, 6, and 9 weeks after restart; continue in intervals of every 12 weeks thereafter. If ECHO does not recover within 3 weeks: Consider cardiology consultation. Permanently discontinue study treatment. Repeat ECHO after 3, 6, and 9 weeks or until resolution or 	
Resting LVEF 39% to 20% or >20% absolute reduction from baseline	 plateau. Inform the Sponsor's medical monitor. Permanently discontinue study treatment. 	
Resting LVEF <20%	Consult with a cardiologist.Repeat ECHO after 3, 6, and 9 weeks or until resolution.	

 Table 18:
 Suggested Action and Dose Modification for LVEF Decrease

ECHO=echocardiogram; LVEF=left ventricular ejection fraction; LLN=lower limit of normal.

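### The protocol lists ECHO/MUGA among its safety measures and names LVEF decrease as a risk, but the SAP plans no analysis of it and does not record the change

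*SAP*

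**What the plan says.** **Protocol, risk.** Section 8 lists among the events that the mechanism of action may cause "LVEF decrease, potential arrhythmias, visual disturbances, and liver enzyme elevation". It adds that "liver toxicities and LVEF decrease will be closely monitored, evaluated, and managed during the study". Section 1.5 notes that symptom-free LVEF decrease was seen with another ERK inhibitor.

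**Protocol, measurement.** Appendix 8 says "ECHO or MUGA scans will be performed to assess cardiac ejection fraction in regular intervals" and, in Table 18, attaches suggested actions to numeric LVEF values and to absolute falls from baseline. Section 9.4.5 and Tables 11 and 12 schedule scans at screening, every 2 cycles for the first 4 cycles, every 4 cycles after that, and at treatment termination. An LVEF below 50% is an exclusion (Section 5.3).

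**Protocol, analysis.** Section 11.7 says that safety will be assessed by several measures, ending with "vital signs, ECOG performance status, ECGs, and ECHO/MUGA scans". The synopsis agrees. Section 11.7 specifies no table or listing for ECHO/MUGA.

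**SAP.** Section 1.0 gives the SAP precedence over the protocol's analysis plan. The list of safety measures in Section 7.6 stops at ECGs and leaves out ECHO/MUGA. Section 7.6.10 reads in full: "Data will be preserved in a Study Data Tabulation Model (SDTM) dataset. No particular analysis will be conducted". No ECHO/MUGA listing is among those named in Section 7.0. Section 7.9, Changes from Protocol, is silent on the point.

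**The concern.** Safety is a primary objective of Phase 1, and LVEF is one of a few toxicities with its own risk statement, eligibility threshold, scan schedule and management appendix. It is measured as a number at set times so that falls without symptoms can be seen. Under the SAP as written, those numbers are stored but not summarised.

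What remains is the adverse event record. It shows which results an investigator judged clinically significant. It does not show where LVEF started, how low it went, how far it fell, or how many subjects had a second scan from which a fall could have been detected. A report built on this SAP could describe the LVEF adverse events, but not the distribution of LVEF change on ASTX029.

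There is also a point of documentation. The two documents disagree on whether ECHO/MUGA is a safety assessment. The section meant to list such differences records one as small as a renamed table heading, but not this one.

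**Working it through.** The plan gives no figure to reproduce here, so the check compares the passages and then looks at what the scan schedule can deliver.

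**1. Is the assessment carried over?**

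| Item | Protocol | SAP |
|---|---|---|
| ECHO/MUGA listed as a safety measure | Yes (11.7, synopsis) | No (7.6) |
| Output specified | None named | Expressly none (7.6.10) |
| Difference recorded | not applicable | No (7.9) |

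The SAP takes precedence, so the working position is no analysis.

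**2. How are the other safety measures treated?** The SAP plans shift tables for ECOG status (7.6.9) and out-of-range proportions for vital signs (7.6.7). ECGs get a listing with optional QTcF summaries (7.6.8). Physical examination (7.6.11) gets the same sentence as ECHO/MUGA, but it stays in the 7.6 list and does not yield a single number with thresholds attached. LVEF does.

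**3. What reaches the adverse event tables?** Protocol 9.3.1 and 9.4.5 have clinically significant ECHO/MUGA findings recorded as adverse events, on the investigator's judgement. SAP 7.6.2 tabulates treatment-emergent events by preferred term and grade. It also tabulates events leading to discontinuation, delay, interruption or dose reduction. Capture is therefore partial, and it is likely to be best where a fall changed treatment.

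**4. What do those tables lack?** They contain no baseline LVEF, worst post-baseline LVEF or maximum decrease. The Safety Analysis Set counts everyone dosed, so it is not the denominator for a fall. That denominator is the subjects with a baseline scan and at least one later scan.

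**5. How complete would the LVEF data be?** With 21-day cycles, the first two on-treatment scans fall at 2 × 21 = 42 days (6 weeks) and 4 × 21 = 84 days (12 weeks). Counting onward from Cycle 4, the next falls at Cycle 4 + 4 = 8. Protocol 9.4.12 leaves assessments after Cycle 6 to the investigator, and its stated minimum does not include ECHO/MUGA. Every routine scan after the Cycle 4 scan is therefore in the discretionary period. The treatment termination scan remains required (9.4.13). The extension schedule (Table 13) has no ECHO/MUGA row.

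**6. Can the Table 18 rows serve as summary categories?** Not as they stand. The first row covers resting LVEF of 49% to 40%, a fall of more than 10 but less than 19, and a value below the institution's lower limit. The second covers resting LVEF of 39% to 20%, or a fall of more than 20. Taking the first row's conditions together, a fall from 65% to 46% is 65 − 46 = 19 points. That is not less than 19 and not more than 20, and 46% is not within 39% to 20%, so no row applies. A fall from 55% to 35.5% is 19.5 points, but it is covered by the second row through its LVEF value. The gap therefore exists for falls of 19 to 20 points when resting LVEF is 40% or above.

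**The case against.** The strongest reply is that little of clinical importance is lost. A fall large enough to interrupt or stop treatment under Appendix 8 is unlikely to be called not clinically significant, so it should be reported as an adverse event and appear in the tables. The clause in Protocol 9.3.1 that excludes non-significant abnormalities applies to laboratory results, not to ECHO. The scans also serve individual care through eligibility and dose modification, and the DSRC reviews emerging safety data. The Phase 1 primary endpoint is DLTs and adverse events, not LVEF. The data stay in SDTM, SAP 7.0 allows further listings, and the table specifications are in a separate document.

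Much of this stands, and it rules out three stronger readings that a reader might infer:

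- **That LVEF events would be invisible.** The adverse event route is real and will often capture actionable falls.
- **That the SAP deletes a promised table.** Protocol 11.7 names the assessment but specifies no output, so the SAP fails to carry out a stated assessment and no more.
- **That the sponsor chose to rely on adverse event reporting.** SAP 7.6.10 gives no reason.

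The reply does not remove the gap. Judgement-based reporting cannot supply the measured values or the denominator. A listing that may be produced is not a commitment, and a separate specification document would have to contradict 7.6.10 to fill the gap.

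**Conclusion.** The point holds as an inconsistency between the documents and an unsummarised safety measure. The protocol says that safety is assessed by ECHO/MUGA among other measures. The SAP drops it from the list, rules out analysis, and does not declare the change.

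The SAP commits to no LVEF summary or listing in a study expected to enrol up to 300 evaluable subjects (about 120 in Phase 1 and up to about 180 in Phase 2). A reader might want this turned into a number of missed cardiac events. The documents do not support one, because they give no LVEF event rate for ASTX029 and no rate at which LVEF falls are reported as adverse events. Nor should LVEF be described as measured throughout, since the schedule is firm only to Cycle 4 and at treatment termination.

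The primary efficacy test and the DLT-based dose decisions are unaffected. The conclusion rests on SAP precedence over the protocol (SAP 1.0) and on 7.6.10 being followed as written.

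**What to change.** 1. Restore ECHO/MUGA to the list of safety measures in SAP 7.6.
2. Replace the sentence in SAP 7.6.10 with a by-subject listing and a descriptive summary by cohort and total on the Safety Analysis Set. Show baseline LVEF, worst post-baseline LVEF, maximum decrease from baseline, and the number of subjects with at least one post-baseline scan, which is the denominator for change.
3. Add counts in categories that neither overlap nor leave gaps. For worst LVEF: 50% or above, 40% to below 50%, 20% to below 40%, below 20%. For maximum decrease: 10 points or less (including none), more than 10 up to 20, more than 20. Label these as descriptive and not as the Appendix 8 rules, which also involve the institution's lower limit of normal.
4. State in 7.6.10 that scans after Cycle 6 are discretionary and that the extension schedule has none, so later data will be incomplete.
5. If no analysis is truly intended, record and justify that in SAP 7.9 instead.

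The cost is a small amount of programming on data already bound for SDTM. No extra scans, subjects or tests are needed.

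Separately, the sponsor should reconcile the rows of Protocol Table 18 for falls of 19 to 20 points with resting LVEF at 40% or above, and reconcile the scan schedule in Section 9.4.5 with Section 9.4.12. How those are resolved is a clinical decision outside this review.

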#### 7.6.11 Physical Examination

Physical examination data will be preserved in a SDTM dataset. No particular analysis will be conducted.

## 7.7 Handling of Missing Data and Other Data Anomalies

No missing data imputations are planned for the study, except for selecting treatment emergent AEs as specified in Section 7.6.2, and for inclusion in concomitant medication analysis as specified in Section 7.6.5. Subjects lost to follow-up will be included in statistical analyses to the point of the data cut-off date.

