9.4.15. Long-Term Follow-up of Health Status

For subjects who remain on study, beginning 3 months after the discontinuation of study treatment, the subject's health status will be collected by telephone every 3 months until death, or the subject withdraws consent, or until the end of the study, whichever occurs first. The following health information will be collected and recorded in the source documents and eCRF:

- Survival information.
- Date of disease progression if subject did not have disease progression at the time they discontinued study treatment.

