11.11. Procedures for Handling Missing, Unused, and Spurious Data

No imputation of values for missing data will be performed unless specified otherwise in the statistical analysis plan. Data from subjects lost to follow-up will be included in statistical analyses to the day of last contact.

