## 1.0 INTRODUCTION

The purpose of this document is to provide details of the planned analyses for the Phase 1 and 2 ASTX029-01 study. The study is to assess the safety, PK, pharmacodynamics, and preliminary clinical activity of ASTX029 administered orally to subjects ≥18 years of age with advanced solid malignancies who are not candidates for approved or available therapies.

The primary objectives of the Phase 1 portion of this study are to assess safety and to identify the MTD, the RP2D, and the recommended dosing regimen of ASTX029 administered orally. The primary objective of the Phase 2 portion of this study is to assess preliminary clinical activity, as determined by objective response rate (ORR) in tumors characterized by gene aberrations in the MAPK signal pathway that may confer sensitivity to ASTX029.

The analyses specified in this document supersede the high-level analysis plan described in the protocol. Analyses and statistical reporting for ASTX029-01 subjects, with the exception of the analyses that are described in a separate Pharmacometrics Analysis Plan (PAP), will be conducted by Taiho Oncology Biostatistics department using SAS version 9.4 or higher.

This Statistical Analysis Plan (SAP) is based on the ASTX029-01 protocol amendment 5.0 (dated 14 April 2022).

Specifications for data tables, listings and figures are detailed in a separate document.

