### 7.5.2 Duration of Response

Duration of response will be calculated for all responders from the date of the first documentation of CR or PR to the date of progress or death, whichever occurs first. Duration of SD will be calculated for subjects whose best response is CR, PR, or SD from the day study drug was first taken to the date of disease progression or death, whichever occurs earlier, or the last disease assessment for subjects without disease progression or death.

Duration of response and duration of SD will not be estimated for subjects who leave the study prior to a first assessment of response nor for subjects whose best response is progressive disease.

Duration of response and duration of SD will be analyzed using a K-M method, with the duration being censored at the time of the date of study termination for subjects without a relapse or disease progression. Duration of response and duration of SD will be summarized.

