#### 7.5.3 Survival

The OS is defined as the number of days from the day study drug was first taken to the date of death (regardless of cause). Subjects without a documented death date will be censored on the last date they were known to be alive. The OS will be presented using a Kaplan Meier estimate. The 95% CI for median OS will be provided using the Kaplan-Meier method with the log-log transformation. All subjects in the Efficacy Analysis Set (Section 5.3) will be included in the OS analysis. The OS rate at 3, 6, 9 and 12 months (and in subsequent 6-month increments if there are participants still at risk) will be estimated with corresponding two-sided 95% CIs.

Frequency (number and percentage) of participants with death events and censoring reasons will be presented with the overall event and censor rates. The event and censoring reasons are as follows:

- Death
- Ongoing and no death
- Withdrawal of consent
- Lost to follow-up.

The OS time or censoring time and the reasons for censoring will also be presented in a listing

The PFS is defined as the number of days from the start of the study drug to disease progression or death, whichever occurs first. The PFS will be analyzed using a Kaplan-Meier method, with PFS time being censored on the date of the last disease assessment. The 95% CI for median PFS will be provided using the Kaplan-Meier method with the log-log transformation. All subjects in the Efficacy Analysis Set (Section 5.3) will be included in the PFS analysis.

Progression of disease (PD) is included as an overall response in Table 1 above, and combines evaluation target, non-target, and new lesions. Target lesion response of PD is at least a 20% increase in the sum of diameters of target lesions, taking as reference the smallest sum on study (this includes the baseline sum if that is the smallest on study). Non-target lesion response of PD is unequivocal progression of existing nontarget lesions. The appearance of 1 or more new lesions is also considered progression of disease. Additional details can be found in Appendix 3 of the protocol, which is based on RECIST v1.1 (Eisenhauer et al 2009).

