## 7.6.4 All-cause Mortality

The percentage of 30- and 60-day all-cause mortality will be calculated based on each subject's date of death relative to C1D1 (ie, date of death minus date of C1D1).

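### SAP 7.7 runs subjects lost to follow-up to the data cut-off, against Protocol 11.11 and SAP 7.5.3 and undeclared in SAP 7.9; OS and PFS are safe if 7.5.3 is followed, but DOR and duration of SD have no clear protection

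*SAP*

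**What the plan says.** On subjects lost to follow-up in general, the two documents give different end dates. SAP 7.7: "Subjects lost to follow-up will be included in statistical analyses to the point of the data cut-off date". Protocol 11.11: "Data from subjects lost to follow-up will be included in statistical analyses to the day of last contact". SAP 1.0 ranks the documents: "The analyses specified in this document supersede the high-level analysis plan described in the protocol". SAP 7.9, which lists changes from the protocol, records a renamed table label, the regimens that were not opened and an added analysis set. It does not record this change.

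For individual endpoints, the SAP sets its own dates:

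- OS (SAP 7.5.3): "Subjects without a documented death date will be censored on the last date they were known to be alive". Loss to follow-up is one of the listed censoring reasons. Protocol 11.6.3 uses the same date.
- PFS (SAP 7.5.3): "with PFS time being censored on the date of the last disease assessment". Protocol 11.6.2 agrees.
- DOR and duration of SD (SAP 7.5.2): Kaplan-Meier, "with the duration being censored at the time of the date of study termination for subjects without a relapse or disease progression". Protocol 11.6.4 ends both at the last disease assessment when there is no relapse, progression or death.
- Early mortality (SAP 7.6.4): "The percentage of 30- and 60-day all-cause mortality will be calculated based on each" subject's date of death counted from C1D1. No rule covers subjects whose status on that day is unknown.

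**The concern.** A subject who is lost cannot be seen to die or progress afterwards. Keeping that subject in the risk set until the cut-off adds person-time in which no event could be recorded. This lowers the apparent hazard and can only raise the Kaplan-Meier curve, so any error favours the drug.

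The SAP contains two rules that give different dates for the same lost subject, and no sentence says which prevails. The protocol does not settle it, because the SAP supersedes the protocol's analysis plan. At stake are the secondary time-to-event summaries: median OS and PFS, the OS rates at 3, 6, 9 and 12 months, DOR and duration of SD.

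**Working it through.** **Step 1. Set the dates side by side for a subject lost before cut-off with no event recorded.**

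| Quantity | SAP endpoint rule | Protocol | SAP 7.7 read literally |
|---|---|---|---|
| OS | last known alive (7.5.3) | last known alive (11.6.3) | cut-off |
| PFS | last disease assessment (7.5.3) | last disease assessment (11.6.2) | cut-off |
| DOR | study termination (7.5.2) | last disease assessment (11.6.4) | cut-off |
| Duration of SD | both last disease assessment and study termination appear in 7.5.2 | last disease assessment (11.6.4) | cut-off |
| 30/60-day mortality | none (7.6.4) | none | no effect on a crude percentage |

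For OS and PFS an explicit SAP rule gives an earlier date than 7.7. For DOR the endpoint rule is itself late, so 7.7 reinforces it. For duration of SD, 7.5.2 gives the last disease assessment where it describes the calculation and study termination where it describes the Kaplan-Meier analysis.

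**Step 2. What would happen to OS if 7.7 displaced 7.5.3.** The documents state no survival assumption and no loss rate, so there is no plan figure to reproduce and every input below is assumed.

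*Model A: early losses.* Exponential OS, follow-up uniform on 6 to 30 months, and a designated fraction given a loss time uniform on months 1 to 6. Kaplan-Meier was computed both ways on large simulated samples. Censoring at loss recovers the truth. With a true median of 8 months and a true 12-month OS of 0.35, carrying lost subjects event-free to cut-off gives:

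| Designated losses | Median (months) | 12-month OS |
|---|---|---|
| 5% | 8.3 | 0.37 |
| 10% | 8.6 to 8.7 | 0.39 |
| 20% | 9.5 | 0.43 |

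*Model B: losses spread over time.* Exponential OS with hazard λ and independent exponential loss with rate η. Under the cut-off rule the apparent hazard at time t is

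λ × P(T>t, L>t) / [P(T>t, L>t) + P(lost before death by t)].

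Worked case, true median 9 months and 20% lost by 12 months in the absence of death:

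- λ = ln 2 / 9 = 0.0770; η = −ln(0.8)/12 = 0.0186.
- At 12 months, P(T>t, L>t) = exp(−0.0956 × 12) = 0.317.
- Lost before death by then = (0.0186/0.0956) × (1 − 0.317) = 0.133.
- Apparent hazard = 0.0770 × 0.317/(0.317 + 0.133) = 0.054, against a true 0.077.

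Integrated over time, the median becomes 10.1 months instead of 9, and 12-month OS 45.0% instead of 39.7%. Over true medians of 6, 9 and 12 months and losses of 5%, 10% and 20%, the median rises by 0.1 to 2.2 months (about 2% to 18%) and 12-month OS by about 1 to 6 percentage points. Simulated cohorts of 29 (true median 9 months) agree: mean 12-month OS is 40.9%, 42.3% and 45.1% under the cut-off rule, against 39.6%, 39.6% and 39.9% with censoring at last contact.

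**Step 3. DOR and duration of SD.** The same mechanism applies, but to every subject without progression or death, not only those lost. After Cycle 4, scans are nominally 4 × 21 = 84 days apart (Protocol 9.1). Censoring at study termination can therefore add unassessed time even for a subject still on schedule, and much more for one who was lost. No size is given here, because the documents offer no basis for a DOR assumption.

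**Step 4. Mortality percentages.** A subject lost on Day 20 has no death date, so the 7.6.4 percentage leaves that subject in the denominator as a non-death on Day 60. This is equally so under the last-contact wording of Protocol 11.11, so the cause is the crude percentage and not 7.7. Under Protocol 9.4.15, "the subject's health status will be collected by telephone every 3 months until death", starting 3 months after treatment ends. A later call can settle Day-60 status for some subjects, but not for those who are lost.

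**The case against.** The strongest reply is that 7.5.3 is the specific rule and would normally govern over a general sentence in a missing-data section. It lists loss to follow-up as an OS censoring reason, so lost subjects are already provided for. The supersession clause ranks the SAP over the protocol; it does not rank 7.7 over 7.5.3. In addition, 7.7 names no endpoint and no censoring date. It can be read as saying only that lost subjects are kept and their data up to the cut-off are used. It also opens by ruling out imputation apart from two date-related exceptions, and treating a lost subject as alive to the cut-off would amount to imputing survival status.

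Most of this stands. A reader might infer that the plan overstates OS and PFS. The documents do not support that: under 7.5.3 the bias is zero, and the Step 2 figures apply only if a programmer uses 7.7 in its place. The Model A figures also depend on all losses falling early. A reader might also infer that 7.7 causes the mortality problem, which Step 4 shows it does not.

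Two things survive. A sentence that can be read either as a data-inclusion rule or as an end date, where the protocol gave a clear end date, needs rewording. And the specific-rule argument does not help DOR, because its specific rule is the late one. Study termination is not defined there. If it means each subject's own exit from the study, the added time is shorter, but it still runs past the last assessment.

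**Conclusion.** The contradiction among SAP 7.7, Protocol 11.11 and SAP 7.5.3 is real and undeclared. It is a wording conflict to reconcile, not a demonstrated bias in OS or PFS. The overstatement is conditional on 7.7 being applied in place of 7.5.3, and its size rests on assumed exponential survival and assumed loss rates.

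The more direct exposure is DOR and duration of SD. For DOR, 7.5.2 itself moves the censoring date from the last disease assessment to study termination, also without mention in 7.9. For duration of SD, 7.5.2 states both dates.

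The reach is limited to secondary, descriptive, single-arm endpoints and, as a separate matter, one safety summary. ORR and the Simon decision (at least 2 of 10, then at least 6 of 29) use no censored time.

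**What to change.** Before database lock:

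1. In SAP 7.7, replace the data cut-off date with the day of last contact, and add that time-to-event endpoints are censored as in Sections 7.5.2 and 7.5.3.
2. In SAP 7.5.2, change the censoring date for DOR and duration of SD to the last disease assessment, as in Protocol 11.6.4. Without this, the cross-reference in item 1 would endorse the late date. If the sponsor prefers to keep a different date, declare and justify it in 7.9.
3. Separately, in SAP 7.6.4, report the number of subjects whose vital status at Day 30 and at Day 60 is unknown, so that they are not silently counted as alive.

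The cost is a few sentences and one extra count in a table, with no new data collection. Reported durations may come out slightly less favourable.
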